SBP	Systolic Blood Pressure
TIA	Transient Ischemic Attack

DEFINITIONS

Cerebrovascular accident (CVA) or stroke: Focal irreversible brain injury with neuron cell death most commonly caused by compromise of end-organ oxygen supply due to parenchymal hemorrhage from loss of arterial vascular integrity or flow interruption from intracranial arterial occlusion.

Transient ischemic attack (TIA): Focal neurological symptoms that resolve spontaneously within 24 hours without evidence of cerebral infarction.

Secondary hypertension: High blood pressure that is caused by an identifiable secondary medical condition or exogenous substrate. Secondary hypertension differs from the usual type of high blood pressure (essential hypertension), which is often referred to simply as high blood pressure. Essential hypertension, also known as primary hypertension, has no clear cause and is thought to be linked to genetics, poor diet, lack of exercise and obesity. Secondary hypertension has been linked to conditions that affect kidney function, as well as sleep apnea, renal circulation compromise, congenital aortic abnormalities, unusual adrenalin secreting tumors, and endocrine system abnormalities. In addition, the aggravating factor for secondary hypertension could also be medications like NSAIDs.

Vulnerable plaque: An atheromatous plaque in an arterial wall that has abundant macrophages, prominent lipid pool, and is usually covered by a thin fibrous cap that is providing a limiting protective barrier from rupture. The repeated cycle of rupture and healing is regarded as one of the key mechanisms of arterial stenosis progression in atherosclerotic heart disease, myocardial infarction and strokes.

Clinical significant structural valvular cardiac disease: For the purpose of this study we define a “significant” valvular condition as any structural heart abnormality that increases the patient’s risks for a stroke or adverse event during the follow-up period. For example, patients with hemodynamically significant aortic stenosis as defined by a mean gradient of > 30mmHg and/or symptoms of dyspnea, chest pain or syncope. In addition, this includes patients with moderate to severe mitral stenosis based on contemporary echo or hemodynamic guidelines.

Moderate to severe reactive airway disease:

Moderate persistent asthma: Documented primary reactive airway disease with symptoms that occur daily. In addition, flare-ups can occur, increasing the symptoms from moderate to severe, which often last several days. Thus any patient with chronic daily symptoms and or documented flare-ups over the last year falls in this exclusion definition. Coughing and wheezing may disrupt the normal activities and make it difficult to sleep. Nighttime flare-ups may occur more than once a week. In moderate persistent asthma, lung function is roughly between 60% and 80% of normal, without treatment.

Severe persistent asthma: With severe persistent asthma, symptoms occur daily and often. They also frequently curtail the patient’s activities or disrupt his/her sleep. Lung function is generally less than 60% of the normal level without treatment. History of hospitalization within the preceding year for an asthmatic attack is also consistent with severe asthma.

Moderate to severe COPD:

Moderate COPD: For the purpose of this study, moderate COPD will be defined as any patient with documented chronic lung disease that experiences daily dyspnea symptoms and requires daily medical treatment in order to maintain normal daily activities.

Severe COPD: Any patient with documented COPD on lung function and/or X-ray studies that has persistent limiting symptoms due to dyspnea. In addition these patients frequently have orthopnea that would prohibit them from lying flat during the needed imaging and transcatheter study device placement. This will also include any patient who has been hospitalized with acute exacerbation of COPD in the preceding year.

Moderate to severe primary pulmonary hypertension: Any patient with symptoms of dyspnea and known pulmonary hypertension without secondary cause of recurrent pulmonary embolism, sleep apnea, left sided heart failure, chronic lung disease or other primary substrate. Objectively this can be defined as NYHA II or III symptoms with mPAP >41mmhg, or PASP >49 in the absence of a secondary cause.

1.0 PROTOCOL SYNOPSIS

TITLE	CALM-FIM_US - C ontrolling and L owering Blood Pressure with the M obiusHD™ - A Prospective Multicenter Safety Study
STUDY OBJECTIVE	To evaluate the safety and performance of the MobiusHD system in subjects with resistant hypertension.
STUDY DESIGN	
This is an open-label, multicenter, first-in-man clinical trial to be conducted inside the United States. Eligible subjects with stage 2 resistant systemic arterial hypertension currently being treated with a minimum of three (3) anti-hypertensive drugs, who consent to study participation will be assigned to treatment with the MobiusHD system.
 
Potential study participants will be consented and then screened at two (2) baseline visits beginning at least 30 days prior to MobiusHD placement. Qualified patients will undergo placement of the MobiusHD under angiographic visualization, and will then be followed for 36 months.
 
Subjects will be enrolled in two (2) phases, as follows:
 
 ▪ Ten subjects will be implanted unilaterally and followed for seven (7) days. ▪ Based on consensus following 7-day clinical outcome analysis by an independent data safety monitoring board (DSMB), 10 additional subjects will be enrolled and implanted bilaterally.
PATIENT POPULATION	Subjects with resistant hypertension receiving at least three (3) anti-hypertensive medications including a diuretic and with no evidence of extracranial carotid disease or significant great vessel/aortic arch atherosclerotic disease.
NUMBER OF PATIENTS	Twenty subjects are to be enrolled at two (2) to ten (10) U.S. clinical sites.
PRIMARY OUTCOME	Safety: Incidence of serious adverse events (SAEs) and unanticipated adverse device effects (UADE) reported for the study population from implantation through six (6) months of follow-up.
SECONDARY OUTCOME	Performance: Decrease in office cuff blood pressure (BP).
ADDITIONAL OUTCOMES	
Change in heart rate
 
Reduction of medication post 6-month follow-up
 
365-Day safety and efficacy
 
Long term safety and efficacy – one (1) to three (3) years

INCLUSION CRITERIA	
Baseline Screening Visit 1 – (Day 0 – 14) – Assessed on Day 14
 
1. Provided written informed consent;2. ≥ 18 years of age and ≤ 80 years of age;3. Office cuff SBP ≥ 160 mmHg measured per protocol instructions (Appendix IV) following at least one (1) month of maximally tolerated therapy with at least three (3) anti-hypertensive medications, of which at least one (1) must be a diuretic. Any combination medications will be counted per the active ingredient. (For example, Zestoretic (Lisinopril +HCTZ) equals two (2) anti-hypertensive medications);4. Renal artery imaging performed within the last 12 months showing no evidence of renal artery stenosis. Acceptable imaging modalities include renal duplex, magnetic resonance angiography, CT angiography, and selective or nonselective renal angiography depending on trial site diagnostic standards. In the absence of adequate imaging testing this inclusion criteria could also be met by obtaining a renal duplex prior to enrollment, or by performing nonselective renal angiography at the time of device implantation.5. Compliant with medications (self-reported) and daily blood pressure readings – Subject must be minimum 80% complaint with diary entries; and6. For females (with child-bearing potential), a negative pregnancy test, and the use of a medically accepted method of birth control for the duration of the trial. 
Baseline Screening Visit 2 – (Day 15 – 30) - Assessed on Day 30
 
1. No significant obstructive vascular disease or plaque on CTA or MRA of the aortic arch and great vessels;2. Carotid duplex studies demonstrating no obstructive carotid disease or plaque;3. Continued adherence to hypertension medications without anticipated changes and daily blood pressure readings – Subject must be a minimum 80% compliant with diary entries; and4. Continued office cuff SBP ≥ 160 mmHg despite at least one (1) month of maximally tolerated therapy with at least three (3) anti-hypertensive medications, of which at least one (1) must be a diuretic. Any combination medications will be counted per the active ingredient. (For example, Zestoretic (Lisinopril+HCTZ) equals two (2) anti-hypertensive medications). 
Day of Procedure -
 
1. Continued adherence to hypertension medications without anticipated changes and daily blood pressure readings – Subject must be a minimum 80% compliant with diary entries.
-------------------------------	---------------------------------------------------------------------------------------------------------------------------------------------------------------------------------------------------------------------------------------------------------------------------------------------------------------------------------------------------------------------------------------------------------------------------------------------------------------------------------------------------------------------------------------------------------------------------------------------------------------------------------------------------------------------------------------------------------------------------------------------------------------------------------------------------------------------------------------------------------------------------------------------------------------------------------------------------------------------------------------------------------------------------------------------------------------------------------------------------------------------------------------------------------------------------------------------------------------------------------------------------------------------------------------------------------------------------------------------------------------------------------------------------------------------------------------------------------------------------------------------------------------------------------------------------------------------------------------------------------------------------------------------------------------------------------------------------------------------------------------------------------------------------------------------------------------------------------------------------------------------------------------------------------------------------------------------------------------------------------------------------------------------------------------------------------------------------------------------------------------------------------------------------------------------------------------------------------------------------------------------------------------------------------------------------------------------------------------------------------------------------------------------------------------------------------------------------------------------------------------------------------------------------------------------------------------------------------------------------------------------------------------------------------------------------------------------------------------------------------------------------------------------------------------------

EXCLUSION CRITERIA	Baseline Screening Visit 1 – (Day 0 – 14) – Assessed on Day 14 
1. Known or clinically suspected baroreflex failure or autonomic neuropathy;2. Hypertension secondary to an identifiable and treatable cause other than sleep apnea (e.g., hyperaldosteronism, renal artery stenosis, pheochromocytoma, Cushing's disease, coarctation of the aorta, hyperparathyroidism and intracranial tumor);3. Treatable cause of resistant hypertension including, but not limited to, improper BP measurement, volume overload and pseudotolerance (excessive sodium intake, volume retention from kidney disease, inadequate diuretic therapy), drug-induced or other causes (non-adherence, inadequate doses, inappropriate combinations, NSAIDs, COX-2 inhibitors, cocaine, amphetamines, or other drugs, sympathomimetics, oral contraceptives (confirmed cause of resistant hypertension), adrenal steroids, cyclosporine, and tacrolimus, erythropoietin, licorice (including some chewing tobacco), ephedra, ma haung, bitter orange); and excessive alcohol intake;4. Arm circumference greater than 46cm and/or BMI \geq 40;5. Chronic atrial fibrillation or recurrent atrial fibrillation with episode within the last 12 months;6. Vulnerable plaque or ulceration of any size in the carotid artery or aortic arch;7. History of bleeding complications with dual anti-platelet therapy in the past or has known uncorrectable bleeding diathesis;8. Current use of additional anticoagulation therapy. Examples include vitamin K antagonists like warfarin, direct thrombin inhibitors, direct factor Xa inhibitors, thrombin IIa inhibitors like apixaban, rivaroxaban, dabigatran and etexilate;9. Peptic ulcer disease with documented active ulcer or bleeding within the last year.10. History of allergy to contrast dye that cannot be managed medically;11. History of orthostatic hypotension;12. History of syncope within the last six (6) months;13. History of myocardial infarction or unstable angina within the past three (3) months;14. History of cerebral vascular accident (stroke or TIA) within the past year;15. Severe chronic kidney disease (calculated GFR < 45 ml/min);16. Prior surgery, radiation, or endovascular stent placement in either
-------------------------------	------------------------------------------------------------------------------------------------------------------------------------------------------------------------------------------------------------------------------------------------------------------------------------------------------------------------------------------------------------------------------------------------------------------------------------------------------------------------------------------------------------------------------------------------------------------------------------------------------------------------------------------------------------------------------------------------------------------------------------------------------------------------------------------------------------------------------------------------------------------------------------------------------------------------------------------------------------------------------------------------------------------------------------------------------------------------------------------------------------------------------------------------------------------------------------------------------------------------------------------------------------------------------------------------------------------------------------------------------------------------------------------------------------------------------------------------------------------------------------------------------------------------------------------------------------------------------------------------------------------------------------------------------------------------------------------------------------------------------------------------------------------------------------------------------------------------------------------------------------------------------------------------------------------------------------------------------------------------------------------------------------------------------------------------------------------------------------------------------------------------------------------------------------------------------------------------------------------------------------------------------------------------------------------------------------------------------------------------------------------------------------------------------------------------------------------------------------------------------------------------

carotid region;

17. Clinically significant structural valvular cardiac disease;
18. Moderate to severe reactive airway disease, chronic obstructive pulmonary disease, or primary pulmonary hypertension;
19. Uncompensated congestive heart failure or known severe reduction in left ventricular function (EF < 30%);
20. Uncontrolled co-morbid medical condition that would adversely affect participation in the trial;
21. Non-controlled diabetes mellitus;
22. Active infection within the last month;
23. Co-morbid condition that reduces life expectancy to less than one (1) year;
24. Mental health issues that would prohibit the subject's availability to meet the Protocol requirements;
25. Currently taking an imidazoline receptor agonist or central sympathetic treatment;
26. Enrolled in a concurrent clinical trial;
27. Unable or unwilling to fulfill the protocol follow-up requirements;
28. Subject is a prisoner or member of other protected population;
29. Planned surgery or other procedure within the next six (6) months;
30. Deep venous thrombosis (DVT) within the last year or documented recurrent DVT.

[figure not shown]
[figure not shown]
Baseline Screening Visit 2 – (Day 15 – 30) - Assessed on Day 30

1. ICA lumen diameters < 5 mm or > 11.75 mm within the planned location of the device placement via CTA or MRA;
2. Carotid hypersensitivity detected by carotid massage or typical history, as described in the Protocol (Appendix V); or
3. Significant aortoiliac or common femoral artery disease that will prohibit safe femoral access.

Day of Procedure – Angiographic

1. Evidence of plaque, ulceration or any stenosis on selective carotid angiography performed in orthogonal views. Lumen diameters will be assessed to exclude subjects with ICA lumen diameters smaller than 5 mm or larger than 11.75 mm within the planned location of the device placement;
2. Any angiographic evidence of plaque or ulceration in the aortic arch and/or the supra aortic vasculature;

	

3. Inappropriate anatomy of the carotid bifurcation for deployment of the MobiusHD, including, but not limited to, tortuosity of the extracranial vessels and significant angulation of the common carotid artery bifurcation; or
4. Type III arch or horizontal takeoff of the left carotid from the innominate and any calcification of the carotid bulb.
--	-------------------------------------------------------------------------------------------------------------------------------------------------------------------------------------------------------------------------------------------------------------------------------------------------------------------------------------------------------------------------------------------------------------------------------------------------------------------------------

STUDY ENROLLMENT	
This study will be enrolled based on the following matrix with review of Data Safety Monitoring Board (DSMB) and FDA:
 
Unilateral study safety design:
  
Subject 1
 
•DSMB review of 7-day data 
Subject 2-5
 
•DSMB review of 7-day data 
Subject 6-10
 
•DSMB review of 7-day data of subjects 6-10•Data submitted to FDA for approval of dose escalation to bilateral implantation or continued unilateral implantation of subjects 11-20 
Following enrollment of the initial 10 subjects, based on DSMB review of available data, a determination will be made on whether the safety of the MobiusHD is adequate to support bilateral placement. If the DSMB determines that bilateral treatment is warranted, an interim report with all available clinical data will be submitted to FDA with a request for initiation of bilateral treatment in the remaining 10 study subjects.
 
Bilateral study design: (if approved by DSMB and FDA)
  
Subject 11
 
•DSMB review of 7-day data 
Subject 12-15
 
•DSMB review of 7-day data 
Subject 16-20
 
•DSMB review of 7-day data of subject 16-20
-------------------------	--------------------------------------------------------------------------------------------------------------------------------------------------------------------------------------------------------------------------------------------------------------------------------------------------------------------------------------------------------------------------------------------------------------------------------------------------------------------------------------------------------------------------------------------------------------------------------------------------------------------------------------------------------------------------------------------------------------------------------------------------------------------------------------------------------------------------------------------------------------------------------------------------------------------------------------------------------------------------------------------------------------------------------------------------------------------------------------------------------------------------------------------------------------------------------------------------------------------------------------------------------------------------------------------------------------------------------------------------------------------------------------------------------------------------------------------------------------------------------------------------------------------------------------------------------------------------------------------------------------------------------------------------

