6.1 INCLUSION CRITERIA

Candidates for this study must meet the following criteria to be enrolled in the study, as determined in the following screening and baseline visits:

Baseline Screening Visit 1 – (Day 0 – 14) – Assessed on Day 14

1. Provided written informed consent;
2. ≥ 18 years of age and ≤ 80 years of age;
3. Office cuff SBP ≥ 160 mmHg measured per protocol instructions (Appendix VI) following at least one (1) month of maximally tolerated therapy with at least three (3) anti-hypertensive medications, of which at least one (1) must be a diuretic. Any combination medications will be counted per the active ingredient (for example, Zestoretic (Lisinopril +HCTZ) equals two (2) anti-hypertensive medications);
4. Renal artery imaging performed within the last 12 months showing no evidence of renal artery stenosis. Acceptable imaging modalities include renal duplex, magnetic resonance angiography, CT angiography, and selective or nonselective renal angiography depending on investigator site diagnostic standards. In the absence of adequate imaging testing this inclusion criteria could also be met by obtaining a renal duplex prior to enrollment or by performing nonselective renal angiography at the time of device implantation.
5. Compliant with medications (self-reported) and daily blood pressure readings – Subject must be a minimum 80% compliant with diary entries; and
6. For females (with child-bearing potential), a negative pregnancy test and the use of a medically accepted method of birth control for the duration of the trial.

Baseline Screening Visit 2 – (Day 15 – 30) - Assessed on Day 30

1. No significant obstructive vascular disease on CTA or MRA of the aortic arch and great vessels;
2. Carotid duplex studies demonstrating no obstructive carotid disease;
3. Continued adherence to hypertension medications without anticipated changes and daily blood pressure readings – Subject must be a minimum 80% compliant with diary entries;
4. Continued office cuff SBP ≥ 160 mmHg despite at least one (1) month of therapy at maximally tolerated therapy with at least three (3) anti-hypertensive medications, of which at least one (1) must be a diuretic. Any combination medications will be counted per the active ingredient (for example, Zestoretic (Lisinopril +HCTZ) equals two (2) anti-hypertensive medications).

Day of Procedure -

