1. Continued adherence to hypertension medications without anticipated changes and daily blood pressure readings – Subject must be a minimum 80% compliant with diary entries.

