8.6 BASELINE ASSESSMENT: VISIT 2 (DAY 15-30) – (+45 DAYS)

- Assessment of patient diary;
- Office cuff blood pressure (Note: Office cuff BP recordings must be performed as detailed in Appendix IV);
- Check for orthostatic blood pressure and orthostatic pulse assessments;
- Changes of medication regimen;
- Review and assessment of adverse events;
- CTA scan or MRA to assess exclusion criteria, from root of Aortic artery to intracranial vessels;
- Duplex imaging of the carotid artery;
- Assessment for carotid hypersensitivity;
- 24 hour ambulatory blood pressure measurement (24hr ABPM); and

8.7 BASELINE ASSESSMENTS VISIT 3 (DAY OF PROCEDURE) – ASSESSED ON DAY OF PROCEDURE

- Physical examination;
- Assessment of patient diary;
- Changes of medication regimen;
- Review and assessment of adverse events;
- Office cuff blood pressure (Note: Office cuff BP recordings must be performed as detailed in Appendix IV);
- Digital subtraction angiography – Inclusion/Exclusion criteria;
- Assessment of all Inclusion/Exclusion criteria; and
- Implantation of MobiusHD.

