8.8 BASELINE ANGIOGRAM

After consent, all subjects should complete the baseline assessments outlined in Sections 8.5 – 8.7 and the Schedule of Study Visits and Assessments (Table 7). Subjects who meet all Inclusion/Exclusion criteria should then undergo angiogram according to imaging guidelines to measure and check the remaining Inclusion/Exclusion criteria. If renal duplex, renal MRA, renal CTA or renal angiography was performed in the 12 months preceding screening and showed no evidence of renal artery stenosis then no further work-up is needed. If no workup has been done then an abdominal angiogram in the 20 degree

LAO projection will be done prior to device implantation. During this angiogram procedure, if all Inclusion/Exclusion criteria are met, then the subject may be treated with the MobiusHD.

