be taken and assessment of the subject diary will be reviewed. 24-hour ambulatory blood pressure monitoring will be assessed. The neurological examinations are classified by NIHSS. Assessment for any new or unresolved adverse events will be made and any changes in medication regimen will be recorded.

8.15 180-DAY FOLLOW-UP VISIT (+14 / -14 DAYS)

During the 180-Day follow-up visit, clinical assessment of the subject and evaluation of neurological symptoms will be performed by the study team. Office cuff blood pressure will be taken and assessment of the subject diary will be reviewed. 24-hour ambulatory blood pressure monitoring will be assessed. The neurological examinations are classified by NIHSS. Duplex imaging is done to visualize the sinus and to assess for complications. Assess for any new or unresolved adverse events and record any changes in medication regimen. Assessment for any new or unresolved adverse events will be made and any changes in medication regimen will be recorded.

8.16 365-DAY FOLLOW-UP VISIT (+14 / -14 DAYS)

During the 365-Day follow-up visit, clinical assessment of the subject and evaluation of neurological symptoms will be performed by the study team. Office cuff blood pressure will be taken. The neurological examinations are classified by NIHSS. Assessment for any new or unresolved adverse events will be made and any changes in medication regimen will be recorded.

8.17 LONG TERM FOLLOW-UP VISITS - 18, 24, 30, AND 36-MONTH FOLLOW-UP VISIT (+14 / -14 DAYS)

During the long term follow-up visits after the angiogram/implantation procedure, clinical assessment of the subject and evaluation of neurological symptoms will be performed by the study team. Office cuff blood pressure will be taken. The neurological examinations are classified by NIHSS. Assessment for any new or unresolved adverse events will be made and any changes in medication regimen will be recorded.

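### The only performance outcome is a fall in office BP, in an uncontrolled study that selects on high office SBP; the 24-hour ABPM already scheduled should be listed beside it and the office baseline fixed

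*Combined protocol and SAP*

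**What the plan says.** Section 1.0 (Synopsis) gives the secondary outcome as "Performance: Decrease in office cuff blood pressure (BP". The other listed outcomes are heart rate, medication reduction after six months, and safety and efficacy at 365 days and at one to three years. None of them names a blood pressure measure. Section 4.0 adds systemic and diastolic pressure as goals without a method, and Section 13.0 plans descriptive summaries without defining a change in BP.

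Office SBP is an entry criterion twice. At Visit 1 it must be at least 160 mmHg, "measured per protocol instructions (Appendix IV) following at least one (1) month of maximally tolerated therapy". At Visit 2 Section 6.1 requires "Continued office cuff SBP ≥ 160 mmHg despite at least one (1) month of therapy at maximally tolerated therapy". The day-of-procedure inclusion list has a single item, which begins "Continued adherence to hypertension medications without anticipated changes and daily blood pressure readings" and sets no SBP limit. Section 8.7, however, lists "Assessment of all Inclusion/Exclusion criteria" for that day, and Section 8.8 says "Subjects who meet all Inclusion/Exclusion criteria should then undergo angiogram according to imaging guidelines".

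Table 7 has office BP at Visits 1, 2 and 3 and at every later visit. ABPM appears in Section 8.6 for Visit 2 ("24 hour ambulatory blood pressure measurement (24hr ABPM"). For the Day 90 and Day 180 visits, Sections 8.14 and 8.15 say "24-hour ambulatory blood pressure monitoring will be assessed".

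**The concern.** Subjects enter partly because their office SBP happened to be high at Visits 1 and 2. Later readings fall back towards each subject's own level whether or not the device works. A control arm would show this drift, but every treated subject here is implanted. If Visit 1, Visit 2 or their mean is the baseline, the reported fall therefore contains regression to the mean, and the plan neither limits nor declares it.

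ABPM is a second measure with no entry threshold, already collected before and after implantation, and it is much less exposed to this selection. Leaving it out of the outcomes makes the more exposed measure the only performance result. This matters because Section 8.2 expects effectiveness data that will support later regulatory submissions.

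**Working it through.** The plan gives no SD, effect size or target for BP, so there is no figure of its own to reproduce. From the documents: the 160 mmHg threshold at two visits, 10 subjects per cohort, no control arm, and the visit schedule. Assumed: pre-screening mean true SBP 155 to 170, between-subject SD 12 to 20 and visit-to-visit SD 8 to 15 mmHg, with no device effect.

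**Model.** True SBP T ~ N(mean, between-subject SD). Each reading is T plus visit error. Keep subjects with V1 and V2 both at least 160. The spurious fall from the Visit 1-2 mean to a later reading F is E[(V1+V2)/2 − F | V1 ≥ 160, V2 ≥ 160]. This equals the mean visit error among those selected, which is above zero.

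**Simulation** (4 million subjects per row, independent visit errors; falls in mmHg):

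| Mean / between SD / visit SD | Fall from Visit 1-2 mean | Fall from Visit 3, 160 not re-applied | Fall from either baseline, 160 re-applied at Visit 3 | Below 160 at Visit 3 |
|---|---|---|---|---|
| 155 / 12 / 15 | 8.9 | 0 | 7.4 | 35.9% |
| 160 / 15 / 12 | 4.2 | 0 | 3.3 | 20.6% |
| 165 / 15 / 10 | 2.4 | 0 | 1.85 | 13.7% |
| 170 / 20 / 8 | 1.0 | 0 | 0.7 | 6.8% |

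Over a 48-cell grid of the same ranges, the fall from the Visit 1-2 mean runs from 0.96 to 8.95 mmHg. A separate set of assumptions (means 150 to 170, between-subject SD 12 to 18, visit SD 8 to 12) gives 1.0 to 7.5.

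**Correlated errors between neighbouring visits** (160/15/12, correlation 0.3 to 0.5). Visit 3 then keeps 1.55 to 2.8 mmHg if 160 is not re-applied. If it is re-applied, the fall is 4.3 to 5.05 from Visit 3, against 4.5 to 5.3 from the Visit 1-2 mean. These figures treat the follow-up error as independent, which is reasonable for Days 90 and 180 but not for discharge or Day 7, where the artefact would be smaller.

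**ABPM at Visit 2** (160/15/12). By symmetry the mean standardised office error at Visit 2 among those selected is 4.2/12 = 0.35. The ABPM artefact is 0.35 × ABPM error SD × correlation with that day's office error:
- SD 5, correlation 0.3: 0.35 × 5 × 0.3 = 0.5 mmHg.
- SD 8, correlation 0.5: 0.35 × 8 × 0.5 = 1.4 mmHg.
- Correlation zero: 0.

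**Precision** (160/15/12, n = 10, t = 2.262). The SD of change from Visit 3 is √(12² + 12²) = 17.0. From the Visit 1-2 mean the simulation gives 14.29. The 95% half-widths are 2.262 × 14.29/√10 = 10.2 mmHg and 2.262 × 16.97/√10 = 12.1 mmHg.

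**The case against.** The strongest objection is that little depends on this outcome. The primary outcome is safety, Section 13.0 plans no formal hypothesis testing and presents every CRF field for each subject, and the move to bilateral placement rests on safety review. No error rate, sample size or decision rule uses the BP result, and a flattering choice of baseline would be visible in the profiles. All of this stands, and it sets the severity low.

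The supplied text is also incomplete. Appendices III and IV appear as titles only and Figures 7 and 8 are not shown. A CRF could define the baseline, and averaging rules could lower the visit SD and with it the artefact. The daily diary readings also carry no BP threshold and offer another check. These points limit the concern but do not put ABPM into a listed outcome.

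A reader might infer three stronger things that the documents do not support:
- That an observed fall would be mostly artefact. At the central inputs 4.2 mmHg lies well inside a half-width of 10.2.
- That the missing detail amounts to a countable menu of rival definitions. Any count depends on convention: whether later visits belong to the separate long-term outcomes, and whether diastolic pressure, named in Section 4.0, is an alternative or a companion.
- That Section 8.7 re-applies the 160 threshold on the day of procedure, so that Visit 3 is as biased as screening. The criteria are labelled by visit and Section 8.8 speaks of remaining criteria, which suggests staged checking. The text does not settle it.

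**Conclusion.** The concern holds, as a cheap improvement of low severity. Measured from the selected screening readings, the performance outcome is biased towards a fall by about 1 to 9 mmHg under the assumed inputs with independent visit errors (4.2 at 160/15/12). That is less than the sampling error in a cohort of 10, but it runs in one direction and more subjects would not remove it.

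ABPM from Visit 2 would carry little or none of this (0.5 to 1.4 mmHg at the central inputs if its error is correlated with the office error). Visit 3 escapes it only if the SBP threshold is not re-applied that day and visit errors are independent. Every mmHg figure rests on assumed SDs. The direction rests only on the two-visit threshold, the absence of a control arm, and some visit-to-visit variation.

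**What to change.** 1. List change in 24-hour ABPM systolic BP from Visit 2 to Day 90 and to Day 180 as a performance outcome beside office BP.
2. Prespecify office SBP change at Day 180, shown from both the Visit 3 reading and the Visit 1-2 mean, separately for the unilateral and bilateral cohorts. Flag any medication change before the reading: the Day 180 window is ±14 days, and Section 8.1 allows reduction from the six-month point. State in the report that the change from the Visit 1-2 mean includes regression to the mean.
3. Reconcile the day-of-procedure inclusion list with Sections 8.7 and 8.8 on whether the SBP criterion applies again that day. Under the assumptions above, 7% to 36% of subjects who qualify at Visits 1 and 2 would read below 160 at Visit 3, so the wording affects who is treated as well as the bias.

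The cost is wording only, since every measurement is already scheduled. There are downsides. Visit 3 is a single procedure-day reading with a larger SD of change (17.0 against 14.3 mmHg) and possible anxiety bias in the device's favour. Baseline ABPM is one recording and may keep a small artefact. The reported fall may be smaller. None of these steps replaces a control arm.
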